7 STUDY ENDPOINTS

Primary endpoint

 HIV self-testing uptake defined as the number of HIV self-tests delivered / total number of coupons distributed

Secondary endpoints

- Proportion of HIVST result's recorded / total number of HIVST delivered
- Proportion of paper and electronic coupons delivered
- Number of HIV tests realized / number of HIV tests results non recorded
- Proportion of MSM/TGW with positive HIV self-tests linked to an ART site
- Proportion of negative MSM/TGW linked to PrEP services
- Characteristics of participants recruited (sociodemographic, sexual behavior, utilization of dating application, substance use) in comparison with IBBS 2019 report
- Proportion of participants with 6-monthly repeated HIV testing during 18 months

Outcomes of acceptability and appropriateness will be explored during focus groups: comfort, usefulness, suitability, confidentiality, credibility, advantages and barriers.

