9 STUDY IMPLEMENTATION

Patients participation in the study

Information

Patient participation in this study is voluntary. Each potential participant will be informed individually by research team of the purpose, scope of the study, procedures involved, duration of follow-up, potential risks and benefits and any discomfort it may entail. In addition to oral explanations, a written information sheet will be systematically provided in Cambodian language (see Appendix A).

Consent

If the patient accepts to be enrolled in the study, s/he will sign the paper and electronic consent forms including different consents: global participation, receiving funds, being recontacted by phone, participation in FGD. Informed consent must be obtained before any exam related to the study. Participants may be given, if they wish, a copy of the paper consent form after they sign.

Intervention RDS intervention

The seeds will be recruited at hotspots, online applications and social media networks. Hotspots include steam sauna and spa and gay bars and clubs. Online applications and social media include Facebook groups, twitter, telegram, whatapps and other date applications such as Grindr, Planet Romeo, Hornet, Blued.

Prior to seed recruitment, a consultative meeting will be conducted among pimps (a person who controls sex workers, especially by finding customers for them, and takes some of the money that they earn), procurers (a person who finds sex workers for people who want to have sex with them), high class MSM & TGW, network organizers, social media group organizers in order to optimize the selection criteria of the seeds.

Selection criteria obtained from the meeting with pimps, procurers, high class MSM, network organizers, twitter groups organizer is applied to select the initial seeds that are very likely to lead us to reach a large diversity of MSM&TGW population.

A number of 15 seeds will be selected firstly to ensure the representation of gender, age group, sexual behaviors, and participation in sex work. If necessary, new seeds could be recruited later. Seeds will come to the study site for checking inclusion criteria and receiving information on self-testing, benefits of their participation and recruiting other participants in their networks along

Version 1.1 du 18/04/2022

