Participation to focus groups will be anonymous and voluntary. Participants will be recruited via the interview in the pharmacy and by the external website. Focus groups will be conducted in a dedicated room, facilitated by a researcher in social and human sciences with the help of the project manager, trained to focus groups and using grids describing topics. Each focus group will be composed of 9-10 members for a 60-90 minutes discussion that will be recorded to facilitate retranscription and translation. Records will be deleted at the end of the study.

The topics included in grids for focus groups with MSM and TGW will be:

- Acceptability of the HIV test delivery: confidence and confidentiality, non-judgmental attitude, quality of explanations, location of pharmacies
- Acceptability of the HIV self-testing realization: quality of information and useinstructions, painful or stress experience, solitude feeling, orientation after testing
- Appropriateness of the strategy: usefulness, perception and improvement of the strategy, willingness to repeat the test in 6 months

The topics included in grids for focus groups with pharmacists will be:

- Satisfaction of the HIV test delivery: feeling at ease, time-consuming, contact with participants, logistical issues
- Willingness to sustain the strategy, perception and improvement of the strategy

Withdrawal of consent and loss to follow-up

Consent withdrawal

A participant will be considered to have withdrawn consent if s/he no longer wishes to remain in the study. In this case, a "withdrawal of consent form" could be filled in the external website.

When a participant who withdraws consent explicitly expresses the will that his/her data be removed from the database and his/her laboratory samples be destroyed, the study team will

Version 1.1 du 18/04/2022

carry out such will. When a patient who withdraws consent do not express such will, data and samples collected prior to the date of his/her consent withdrawal will be used for the analysis.

Loss to follow-up

When a participant who has not explicitly withdrawn consent does not return the HIVST result after one week, the research team will reach them by phone. Also, 1 week after returning positive HIVST results, if there is no information confirming the linkage to one of the partner ART sites or participant does not show up after receiving the reminder for 6-month HIVST, the research team will reach them by phone.

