A participant who does not show up for a given schedule and the study team failed to reach by phone will be considered lost-to-follow-up.

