Essential study documents (protocol, case report forms, SOPs, etc) and regulatory (ethical clearance, task delegation, agreements, curriculum vitae, etc..) will constitute the Trial Master File (TMF). The TMF will be held at the GMO located at the UHS and will be retained for 15 years.

Each investigator will keep a hard copy of relevant TMF documents in an Investigator Site File (ISF). The Clinical Research Assistants (CRAs) will be responsible for checking that the documents contained in the ISF of each study site are up-to-date.

Data management

The UHS Team will be responsible, on behalf of the sponsor, for implementation of procedures for data collection, storage, protection, retention and destruction. The team has implemented a data safety and security concept according to the requirements. All related procedures will be developed in cooperation with the data security engineer of the UHS team and have to be approved by the official data protection officer of the University of Health Sciences prior to implementation.

Version 1.1 du 18/04/2022

Data collection

Data from participants will be collected in partner pharmacies, after signature of Informed consent, in tablets on electronic case report forms (e-CRF). The community workers will be responsible for filling out data into the e-CRF. A unique e-CRF will be assigned for each participant. The participant will only be registered through a unique confidential code. A Standard Operating Procedure (SOP) will be provided to guide the community workers to fill out the e-CRF. All information required by the protocol should be provided and any omission would require explanation.

The CRAs are responsible for ensuring that all sections in the e-CRF are completed correctly and that number of entries can be verified with the number of HIVST delivered in each pharmacy. The results of the HIVST will be recorded by the participants on the external website with the unique ID.

Data entry and checking

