14 STATISTICAL ANALYSES

Calculation of number of participants needed

We will use a pragmatic approach with the objective to recruit the maximum of MSM and TGW. According to the IBBS 2019, the estimated number of MSM in Phnom Penh is 6300 and the

Version 1.1 du 18/04/2022

estimated number of TGW is 1400.

With 1500 participants (1000 MSM and 500 TGW), we will be able to estimate an HIV self-test uptake of 70% to within a 95% confidence interval of +/- 2 – 2.5% (width of the confidence interval (in %) = $1.96 \times \sqrt{(p \times (1-p)/n)}$.

Analysis plan

Description of the characteristics at inclusion.

These variables will be described by their median, interquartile range, mean, standard deviation, or frequencies (%), as appropriate. These variables will be compared to those reported in the IBBS 2019 for MSM and TGW.

Primary outcome

The percentage, and its 95% confidence interval of HIV self-tests delivered among the total number of coupons distributed will be given and stratified by gender (MSM or TGW) and by type of coupons (paper or electronic).

Secondary outcomes

- The percentage and its 95% confidence interval of HIVST result's recorded among the total number of HIVST delivered will be given and stratified by gender (MSM or TGW)
- For those accepting to be contacted by phone, the percentage and its 95% confidence interval of HIVST realized among the number of HIV tests results non recorded will be given
- The percentage and its 95% confidence interval of participants with positive HIV selftests linked to an ART site will be given and stratified by gender (MSM or TGW)
- The percentage and its 95% confidence interval of participants with negative HIV selftests linked to PrEP services will be given and stratified by gender (MSM or TGW)
- The percentage and its 95% confidence interval of participants with 6-monthly repeated HIV testing during the 18 months (so 4 HIVSTs during the total duration of the study) will be given
- The probability of discontinuation of HIV testing and its 95% confidence interval, as well as the median time to the occurrence of HIV testing discontinuation, will be determined using a Kaplan Meier analysis, to take into account censored data due to lost of follow-up.

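### The Kaplan-Meier analysis censors unreached participants because they missed a retest, so testing discontinuation is likely underestimated (minor)

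*Protocol*

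**What the plan says.** All references are to the protocol; no SAP is available.

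- **Analysis.** Section 14, Secondary outcomes, plans a probability of discontinuation with a 95% confidence interval and a median time to discontinuation. Both "will be determined using a Kaplan Meier analysis, to take into account censored data due to lost of follow-up". No other reason for censoring is named.
- **Loss to follow-up.** Section 9 says that a participant who "does not show up for a given schedule and the study team failed to reach by phone will be considered lost-to-follow-up". One of the situations that lead to the phone call is that a "participant does not show up after receiving the reminder for 6-month HIVST, the research team will reach them by phone". The others are an HIVST result not returned after one week and a link to an ART site not confirmed one week after a positive result.
- **Phone contact.** It needs its own agreement. Section 9, Consent, describes forms "including different consents: global participation, receiving funds, being recontacted by phone, participation in FGD". Another secondary analysis in section 14 is limited in this way: "For those accepting to be contacted by phone".
- **What is recorded.** Section 13, Data collection: "The results of the HIVST will be recorded by the participants on the external website with the unique ID". Section 9 has the coupon scanned at the pharmacy before a kit is handed over.
- **Neighbouring endpoint.** Section 7 lists "Proportion of participants with 6-monthly repeated HIV testing during 18 months". Section 14 makes this concrete as "so 4 HIVSTs during the total duration of the study".

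**The concern.** Kaplan-Meier estimation assumes that people censored at a given time have the same subsequent risk as those still under observation. Here one route to censoring runs through the missed retest itself. Take two participants who both miss the 6-month test. The one who answers the phone can be counted as having discontinued. The one who does not answer, or who never agreed to be called, leaves the analysis without an event. If the people who leave in this way have mostly stopped testing, the curve is too favourable: the 18-month probability is too low and the median too late.

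Adherence to 6-monthly testing is a secondary objective (section 4). The four-test percentage, if taken over all participants, would count these same people as failures. The report could then show two adherence results that point in different directions, with nothing to explain the gap.

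**Working it through.** The protocol states no figure for discontinuation or loss to follow-up, so there is no figure of its own to reproduce. The calculation below shows direction and sensitivity only.

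**Inputs**
- Three retests after baseline (four tests over 18 months, section 14).
- m: probability of missing each retest. Assumed.
- u: share of missers not reached by phone. Assumed.
- v: share of the unreached who in fact still test, elsewhere or with a study kit whose result was not uploaded. Assumed.
- Missers who are reached count as events. All three retests fall due for everyone.

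**Formulas for 18-month discontinuation**
- True: 1 − [1 − m(1 − uv)]³
- Planned, unreached censored at the due date: 1 − [1 − m(1 − u)]³
- Planned, unreached censored just before the due date: 1 − [1 − m(1 − u)/(1 − mu)]³

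**Case m = 30%, v = 0.** True value: 1 − 0.70³ = 65.7%.

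| u | censored at due date | censored just before | shortfall (points) |
|---|---|---|---|
| 10% | 1 − 0.73³ = 61.1% | 1 − (1 − 0.27/0.97)³ = 62.4% | 4.6 / 3.3 |
| 25% | 1 − 0.775³ = 53.5% | 1 − (1 − 0.225/0.925)³ = 56.7% | 12.2 / 9.0 |
| 50% | 1 − 0.85³ = 38.6% | 1 − (1 − 0.15/0.85)³ = 44.1% | 27.1 / 21.6 |

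True survival is 0.70 at 6 months and 0.49 at 12, so the true median is 12 months. The planned median is 18 months at u = 10%. At u = 50% it is not reached, because the curve ends at 0.614 or 0.559.

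A simulation with 1,500 participants (400 runs, m = 30%, u = 50%) gave 38.5% and 44.0% for the two planned versions against 65.7%, with a standard deviation of about 1.2 to 1.6 points. Under these assumptions the gap is well beyond sampling error.

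**Dependence on v (m = 30%, u = 50%).** The true value is 59.9% at v = 25%, 53.5% at 50%, 46.4% at 75% and 38.6% at 100%. The planned estimate stays at 38.6% or 44.1% throughout.

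**Break-even.** With censoring at the due date, the planned estimate is too low for every v below 100% and exact at 100%. With censoring just before it, setting the two hazards equal gives v = (1 − m)/(1 − mu). At m = 30% this is 0.70/0.97 = 72% (u = 10%), 0.70/0.925 = 76% (u = 25%) and 0.70/0.85 = 82% (u = 50%). Over m from 10% to 50% and u from 10% to 50% it runs from 53% to 95%. Above break-even the bias reverses: at m = 30%, u = 50%, v = 100%, the estimate is 44.1 − 38.6, about 5.6 points too high before rounding.

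**Comparison with the four-test figure.** At m = 30%, u = 50%, v = 0, a share of 0.70³ = 34.3% complete all four tests, while the curve shows 55.9% to 61.4% not discontinued.

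**The case against.** The strongest reply is that the protocol defines neither the discontinuation event nor the censoring date, and a SAP could do so. The missed retest comes before the failed call, so it could be dated as the event before the person becomes lost. Censoring would then apply only to loss by the other routes, such as a baseline result never returned. That reading is possible, but it is not what the text says. Section 14 names loss to follow-up as the reason for censoring, and section 9 brings the unreached non-attender into that category. A SAP that counted these people as events would depart from the stated rule, so the protocol sentence needs correcting.

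Other parts of the reply stand:

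- A reader might infer that recorded results settle who tested, so that only testing outside the study is unknown. The documents do not support this. Section 7 has an endpoint on tests done among results not recorded, and section 14 examines it only in those who accept calls. For an unreached participant who collected a kit, use of that kit is also unknown.
- A reader might infer a bias of 20 points or more. That follows only from u = 50% and v near 0, neither of which is in the protocol. At u = 10% the gap is 3 to 5 points. The model also ignores late tests prompted by a call.
- The curve is not a listed endpoint in section 7, and no sample size or decision depends on it.

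**Conclusion.** The point holds as a minor one. As written, an unreached participant who misses a retest is censored because of the missed retest, so the censoring is informative. Discontinuation is likely underestimated unless most of the unreached still test.

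"Likely" is a judgement, because v is unknown. The nearest information is the survey context in section 3: about half of MSM and one third of TGW reported no test or none in the past 12 months, which leaves about one half and two thirds tested. Both are below the 72% to 82% break-even at m = 30%, but two thirds is not below the lower end of the wider range. They are also general survey figures, not rates among unreached participants.

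The size cannot be derived from the protocol. On the assumptions stated (m = 30%, v = 0) it is about 3 to 5 points at u = 10% and about 22 to 27 points at u = 50%. It would be wrong to extend the point to all censoring, since administrative censoring need not be informative in this way. The primary endpoint and the four-test percentage do not use this censoring and are not affected.

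**What to change.** Amend the Kaplan-Meier item in section 14:

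1. **Risk set.** Start with participants who have a recorded non-reactive baseline result, since they receive the repeat coupon (sections 5, 8 and 9). Report separately those who never returned a baseline result.
2. **Event.** No study retest within a fixed, stated window around each 6-monthly due date, whether or not the participant is reached by phone. A retest is shown by a repeat coupon scanned with a kit delivered, or by an uploaded result. Call this discontinuation of study testing.
3. **Censoring.** Only at the administrative end of follow-up, at withdrawal of consent, or when no repeat test is due because of a reactive result.
4. **Sensitivity analysis.** Keep the version that censors unreached non-attenders. The two results together show how far the conclusion depends on the unreached.

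The cost is a few sentences and no new data collection, because coupon scans and uploaded results are already planned. It should be confirmed that repeat coupons can be tied to the participant's ID.

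There is a downside. Reported adherence will look less favourable and may be conservative for testing outside the study, and section 3 shows that most reported testing takes place through community-based organisations. At m = 30%, u = 50%, v = 50%, and if all of the continued testing is outside the study, the true figure is 53.5%, against 65.7% for study testing and 38.6% to 44.1% for the censored version. Conversely, collecting a kit does not prove that it was used.

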15 SCIENTIFIC COMMUNICATION

All written or oral communications of the study's results must receive the approval of the coordinating investigators and of the SAB of the study.

The GMO will realize data analysis. This analysis will lead to a report, submitted to the SAB for approval. This report will help to prepare scientific publications whose final draft must be approved by the SAB .

All publications will include the name of sponsor as follows ("ANRS-MIE. The French National Agency for Research in HIV/AIDS, Viral Hepatitis and Emerging Infectious Diseases is the sponsor of the project") followed by the ANRS study number (ANRS 0100s + Acronym).

In case of ancillary studies, results will be published after approval by SAB. In addition, these results will be published only after the publication of the main results obtained during the research project. Results obtained through ancillary studies will be also transmitted to ANRS-MIE for information.

16 ETHICS AND LEGAL CONSIDERATIONS

• 16.1. Ethics

This research project will be conducted with regard to fundamental ethical principles that are described in the updated version of the Declaration of Helsinki (64th World Medical Association [WMA] General Assembly, Fortaleza, Brazil, October 2013), and in the ANRS ethics charter for research in developing countries (July 2017) (http://www.anrs.fr/Ressources-et-publications/Publications/Publications-ANRS/Charte-d-ethique-de-la-recherche-dans-les-pays-en-developpement).

• 16.2. Policies and legal aspects

This study will be conducted in conformity with the French Public Health Code, as modified, notably, by Public Health Low no 2004-806 of August 9, 2004 and its subsequent texts, and the Law n° 2012-300 of March 05th 2012 on research involving the human person ('Jardé Law') and its subsequent texts.

This research project will be also conducted in accordance with national regulations and laws in Cambodia, and according to E6 Good Clinical Practice (GCP).

The protocol, information sheet, and informed consent (appendix 1 and 2) will receive the approval from the National Ethics Committee for Health Research (NECHR). The written NECHR approval must be made available to the legal sponsor before the study can start. The sponsor or its delegate is, together with the investigator, responsible for submission to and communication with the NECHR as well as for obtaining approval of all subsequent major changes, in compliance with local law.

The research will be performed according to the present protocol. All researchers and investigators participating to this project will respect the protocol, especially in obtaining informed consent (see below).

Version 1.1 du 18/04/2022

• 16.3. Information and consent

Participation in the study is voluntary. The consent of each potential participant is a prerequisite before starting any sampling or before obtaining any specific information related to the research project. The informed consent must be signed by each participant after giving full research description:

- What is being studied?
- What is the procedure/protocol?
- Who is sponsoring the study?
- What are the risks and burdens?
- What are the benefits?
- Whom to contact with questions/concerns

The person in charge of informed consent process at the trial site will read out and explain the information notice to the patient in his/her language, and will answer any questions that may arise. Each potential participant will be given time to think about the information before making a decision.

Each subject must fully understand that they have the full freedom to accept or refuse to participate in the study. Once one subject is included in the research project, he has to understand that he can also withdraw from it whenever he wants without any problems/consequences and he will continue to benefit from the regular medical care and check-up.

When one person gives his/her consent for participating to the study, he (she) will write his (her) last name and first name, date and sign the informed consent.

Each signed informed consent will be kept in a safe manner and in a safe place for a total duration of 15 years after the end of the research project.

• 16.4. Data confidentiality

All information collected from enrolled subjects will be strictly confidential and coded. Investigators will make individual data available upon request by representatives of the sponsor and representatives of the ethical and regulatory health authorities, for monitoring purposes or in the event of external audit or inspection. Disclosure to other third parties is strictly prohibited. All persons having access to the data, including the investigator, are subject to the obligation of professional secrecy.

During the implementation and by the end of the research, information collected among participants must be de-identified and names, personal addresses must not be indicated in any document brought back to the GMO.

For this purpose, each participant will receive a unique identification number. This code will be the only patient identifier on any document related to the study, as well as in the electronic study database. There will be no link between the name of the patient and his/her personal identifier in the database.

